
 Previous drug treatment in the pre-index period, based on appropriate ATC group level 
 Percentage of patients who received specific treatments (most common 10 treatments as observable for above samples) with at least two prescriptions in the pre-index period. 
Documentation referring to the 12 months follow-up after index date (for patient subgroups: 24 months/36 months follow-up, or complete follow-up period)
 
 For patients with available data resulting from a disease management program (DMP) 
 Weight [kg] (reported MIN, MAX and MEAN during follow-up period) Height [cm] Blood pressure (reported MIN, MAX and MEAN during follow-up period) Non-drug treatment recommendations Exacerbations (number and severity) FEV₁ (reported MIN, MAX and MEAN during follow-up period) Smoking status if applicable Drug treatment with long-acting bronchodilators (incl. separate reporting for respective agent classes beta-agonists, anticholinergics, methylxanthines) Drug treatment with short-acting agents Drug treatment with anti-inflammatory drugs (ICS, PDE-4, macrolides) Top-10 prescribed non-COPD drug therapies (based on ATC codes on appropriate level) 			

Name of company: Boehringer Ingelheim			
Name of finished medicinal product: COPD medication of any type			
Name of active ingredient: COPD medication of any type, ATC code R03			
Protocol date: 16 Oct 2019	Study number: 1237-0092	Version/Revision: 1.0	Version/Revision date: Not applicable

 • Antibiotics for systemic use (based on ATC J02AA) • Antibiotics in combination with corticosteroids (based on ATC D07C) • Systemic/oral corticosteroids (SCS/OCS; based on ATC R01AD02; D07AA01; D10AA02; H02AB04) • All-cause hospitalizations 
 ○ Among them: hospitalizations with COPD as main diagnosis (ICD-10 J44.-) • Among them: hospitalizations with a COPD exacerbation as main diagnosis (ICD-10 J44.1) • Exacerbations as documented by outpatient pneumologists (ICD-10 J44.1) • GP visits and pneumologists' visits and visits to other specialists • Prescription of COPD-associated aids 
 ○ Oxygen therapy • Date of death, if patient died during follow-up period (for censoring and time to event analyses). 			

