 - According to both guidelines mentioned above, a triple combination treatment LABA+LAMA+ICS should only be prescribed if a patient experienced at least two exacerbations or one severe exacerbation requiring an inpatient treatment in the history of the disease. Based on this, the following percentage will be reported:
 - Percentage of patients not treated in line with the 2012/2018 guideline
 - Only 1 or less confirmed outpatient diagnoses and no inpatient diagnosis of a COPD exacerbation (ICD-10 J44.1) before date of prescription of a triple therapy.
- COPD-12, for the whole follow-up period (12 months)
 - A treatment intensification (mono to dual therapy, mono to triple or dual to triple therapy) should generally be accompanied by a thorough application of recommended diagnostic measures, according to the 2012/2018 guidelines. For these, typically, general practitioners (GPs) do not have the necessary infrastructure. Based on this, the following percentage will be reported:
 - Percentage of patients who received a treatment intensification without any previous visit of a pneumologist or hospital (same quarter or previous quarter)

Sensitivity analysis

In a first sensitivity analysis, those of above patients will be included for whom at least one ICD-10 COPD code that provides information up to the 5th level is documented: These subcodes include information about FEV₁ level. For patients for whom such a subcode is available, in this analysis, disease severity will be defined based on this information, which is mainly important when applying the 2012 guideline.

¹⁶ Of those patients starting with triple therapy of LABA+LAMA+ICS at time of incident COPD diagnosis, physician visits (separately of cardiologists, pneumologists) and measures of lung function (DMP-dataset only) before or at index date will be reported. Time since last physician visits to a cardiologist or a pneumologist will be reported too.

In a second sensitivity analysis, the sample COPD DMP-12 will be analyzed. In the DMP data set, additional documentation about exacerbation history and FEV₁ is available. Based on these data, the following analyses are planned:

- COPD DMP-12, at index date: no additional analysis, as DMP data will not be available for the pre-index period
- COPD DMP-12, at first date of an observed LABA+LAMA+ICS combination, which is not the index date; patients for whom at least one DMP entry before date of prescription of above combination will be included

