 - According to both above guidelines, a triple combination treatment LABA+LAMA+ICS should only be prescribed if a patient experienced at least 2 exacerbations or one severe exacerbation requiring an inpatient treatment in the history of the disease. In addition, the 2012 guideline also recommended such a treatment in case a FEV₁<50% could be observed. Based on this, the following percentages will be reported:
 - Percentage of patients not treated in line with the 2018 guideline
 - Only one or no confirmed outpatient diagnosis and no inpatient diagnosis of a COPD exacerbation (ICD-10 J44.1) before date of prescription of a triple therapy.
 - Percentage of patients not treated in line with the 2012 guideline
 - Only one or no confirmed outpatient diagnosis and no inpatient diagnosis of a COPD exacerbation (ICD-10 J44.1) and only one or no outpatient diagnosis and no inpatient exacerbation diagnoses as documented in the DMP dataset and no documented FEV₁ value <50%.

Second Secondary

Description of exacerbation frequency

For all samples (COPD-12, COPD-24, COPD 36, COPD DMP-12, COPD DMP-24, COPD DMP-36, COPD-FULL DATA), exacerbation frequency in the pre-defined follow-up periods (12 months, 24 months, 36 months, patient-individual follow-up times) will be described. Because of the higher diagnosis validity, in the main analysis only severe exacerbations leading to an inpatient hospitalization (COPD exacerbation documented as main diagnosis: ICD-10 J44.1) will be considered. Moreover, in a separate analysis proxies will be used to estimate non-severe exacerbations. Therefore prescriptions of SCS/OCS either separately or in combination with antibiotics, will be considered as proxy for the treatment of a non-severe exacerbation (without an inpatient hospitalization). Exacerbation frequency (once for severe and once for non-severe exacerbations) will be reported as percentage of patients having experienced at least 1 exacerbation, exactly 1 exacerbation, exactly 2 exacerbations, exactly 3 exacerbations, and >3 exacerbations, and as mean number of exacerbations per observed patient-year.

Third Secondary

Description of health care resource use and direct treatment cost

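### In the COPD DMP-12 triple-therapy analysis, the 2018 rule leaves out the DMP exacerbation history that the 2012 rule uses, although both guidelines are given the same exacerbation criterion

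*Combined protocol and SAP*

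**What the plan says.** Section 9.3.2.2 (First Secondary) compares prescribing with the 2018 guideline and uses the 2012 guideline as a sensitivity variant. In COPD-12, for a first triple combination that does not fall on the index date, one claims rule serves both guidelines: "Only 1 or less confirmed outpatient diagnoses and no inpatient diagnosis of a COPD exacerbation (ICD-10 J44.1) before date of prescription of a triple therapy".

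The second sensitivity analysis moves to COPD DMP-12, and the reason is given: "In the DMP data set, additional documentation about exacerbation history" and FEV1 can be had there, and "Based on these data, the following analyses are planned". Only patients with a DMP record earlier than the triple prescription enter. The exacerbation criterion is stated once for both guidelines: "According to both above guidelines, a triple combination treatment LABA+LAMA+ICS should only be prescribed if a patient experienced at least 2 exacerbations". A single severe episode treated in hospital also meets it. One further element follows: "In addition, the 2012 guideline also recommended such a treatment in case a" FEV1 under 50% is found.

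Two definitions of treatment not in line with the guideline are then set:

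- 2018: "Only one or no confirmed outpatient diagnosis and no inpatient diagnosis of a COPD exacerbation (ICD-10 J44.1) before date of prescription of a triple therapy".
- 2012: the same claims condition without its closing time limit, and "only one or no outpatient diagnosis and no inpatient exacerbation diagnoses as documented in the DMP dataset", and no recorded FEV1 under 50%.

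**The concern.** A criterion described as common to both guidelines is measured from claims for one and from claims plus DMP records for the other, and no reason is given. The guideline that the section uses as its main comparator is the one that does without the DMP history.

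The purpose of the analysis is at stake. The COPD-12 result rests on J44.1 coding alone, and the natural question is whether the share not in line with the 2018 guideline changes once the richer DMP exacerbation record is consulted. As written, the 2018 figure cannot answer that. A patient with qualifying exacerbations in the DMP record but not in claims is still counted as not in line with 2018.

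**Working it through.** The plan states no figure for this analysis, so there is nothing to reproduce. The check sets the rules side by side, then works out the direction and possible size.

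**Step 1: the rules compared (section 9.3.2.2).**

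| Evidence that puts a patient in line | COPD-12, both guidelines | DMP-12, 2018 | DMP-12, 2012 |
|---|---|---|---|
| Claims J44.1 (two outpatient or one inpatient) | used | used | used |
| DMP-documented exacerbations | not used | not used | used |
| FEV1 below 50% | not used | not used | used |
| Time limit written into the rule | yes | yes | no |

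The FEV1 row is the announced difference. The DMP row is not announced. The COPD-12 and DMP-12 2018 columns are the same: for 2018, DMP data decide who enters the analysis but not how anyone is classed.

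**Step 2: direction.** For each analysed triple starter, let c, m and f mean that the claims criterion, the DMP criterion and FEV1 below 50% respectively were met before the first triple prescription. The time limit is read into the 2012 rule here.

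- 2018 as written: A = P(not c)
- 2018 with the DMP term added: B = P(not c, not m)
- 2012: C = P(not c, not m, not f)

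Then A − B = P(not c, m) = d, which cannot be negative. B − C = P(not c, not m, f) = e, the FEV1 component. So A − C = d + e, whereas rules with the same exacerbation evidence would differ by e alone.

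Among patients who do not meet c:

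- m no, f no: not in line under every rule.
- m no, f yes: the rules part because of FEV1, as the plan announces.
- m yes, f no: not in line with 2018 as written, in line with 2012. FEV1 plays no part; the data source alone causes this.
- m yes, f yes: not in line with 2018 as written, in line with 2012, and in line with 2018 if the DMP term is added.

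**Step 3: size.** d = N × r, where N is the share not in line on claims alone and r is the share of these who meet the DMP criterion. The documents give neither, so the values below are assumptions.

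| N | r = 0% | r = 10% | r = 20% |
|---|---|---|---|
| 40% | 0 | 4 | 8 points |
| 60% | 0 | 6 | 12 points |
| 80% | 0 | 8 | 16 points |

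One case in full, also assuming that 20% have FEV1 below 50% and that it is independent of m: with N = 80% and r = 10%, A = 80.0%, B = 80.0 × 0.9 = 72.0% and C = 72.0 × 0.8 = 57.6%. The two percentages as written lie 80.0 − 57.6 = 22.4 points apart. Of these, 72.0 − 57.6 = 14.4 come from FEV1 and 80.0 − 72.0 = 8.0 from the data source.

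**The case against.** The asymmetry could be deliberate. Section 9.9 says the validity of DMP documentation still has to be checked, and the study-size text in the abstract leaves open whether the DMP data are usable at all. Keeping 2018 on claims would hold the main comparator to the better-tested source. That supports reporting a claims-only figure, but it does not explain the difference: the doubt applies equally to the 2012 rule, which uses the DMP data. Table 4 also plans to combine inpatient codes with DMP documentation when exacerbation frequency is analysed in the DMP samples.

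It is also fair to say that the plan never calls FEV1 the sole difference. It names one shared criterion and one addition, and that is how the text reads.

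Three stronger readings are tempting but not supported:

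- **A different time window.** A reader might infer that the 2012 rule admits records after triple start, because it lacks the time limit and the abstract lists DMP exacerbations and FEV1 under "Documentation referring to the 12 months follow-up after index date". That list is a general inventory of variables. Section 9.3.2.2 fixes the assessment, for both samples, on the day triple therapy is first prescribed. The heading of this analysis repeats that, and requiring an earlier DMP record would make little sense otherwise. The missing phrase is best taken as an omission.
- **A DMP term that cannot be programmed.** A reader might infer this because Supplemental Table 1 shows no separate outpatient exacerbation count. But the table shows no FEV1 either, so it is not a full list, and the abstract and sections 9.1 and 9.4 describe exacerbation number or frequency, and severity, as DMP content. What stands is a label mismatch for COP_EXA: the German refers to exacerbations, the English to hospitalizations.
- **A distorted guideline contrast.** No subtraction of the 2012 percentage from the 2018 percentage is planned. Section 7 speaks of two scenarios, and Table 4 compares patients in line with those not in line. The decomposition above matters only to someone who reads the two figures side by side.

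**Conclusion.** The point holds for the source of the exacerbation evidence, which is explicit in the text and does not depend on how the time limit is read. The 2018 percentage in COPD DMP-12 is the COPD-12 claims rule applied to a subsample. It equals or exceeds the percentage with the DMP term by d. The documents do not give d, and it may be 0; 0 to 16 points is the span under the assumed N of 40–80% and r of 0–20%.

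This compares two definitions. It does not establish bias against true guideline adherence, because both rules count recorded diagnoses rather than verified episodes. The time limit and the COP_EXA label are clarifications. It is worth correcting before programming because the rule defeats its own stated purpose, but its reach is limited to this one percentage.

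**What to change.** In section 9.3.2.2, second sensitivity analysis:

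1. Add to the 2018 rule the DMP exacerbation term that already stands in the 2012 rule, so that FEV1 below 50% is the only difference between them.
2. Report the claims-only 2018 percentage in the same patients alongside, so that the effect of the DMP history can be read directly.
3. Repeat the 2018 rule's time limit in the 2012 rule.
4. Reconcile the German and English labels of COP_EXA in Supplemental Table 1.

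If the asymmetry is intended, state the reason instead.

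The cost is the rewording of two rules, one label check and one extra percentage. No new data are needed, since every analysed patient already has a DMP entry before triple start. There are two drawbacks. DMP records of unchecked validity may misclassify some patients under the 2018 rule; the parallel claims-only figure covers this. Restricting to entries before triple start also misses earlier events that were documented only later; this should be stated as a limitation.

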9.9 LIMITATIONS OF THE RESEARCH METHODS

The main limitation of this claims data analysis is the limited availability of clinical information (clinical parameters, prescribed dosages, reasons for prescribing specific agents etc.). Information available in claims data is limited to parameters, which are generally relevant for reimbursement purposes. Clinical parameters will be only available for patients who participate in a DMP, whereas the validity and frequency of these documentations as well as the time of first documentation for incident COPD patients need to be checked. For a substantial part of the patients, these data might not be valid/available.

In addition to that, the available claims dataset will be a regional dataset, which probably covers only the regions of [REDACTED].

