9.3.2 Outcomes? (e.g. International Classification of Diseases (ICD)-10, Medical Dictionary for Regulatory Activities (MedDRA))				
9.3.3 Covariates?				
9.4 Is a linkage method between data sources described? (e.g. based on a unique identifier or other)				

Comments:

Section 10: Analysis plan	Yes	No	N/A	Section Number
10.1 Is the choice of statistical techniques described?				9.7
10.2 Are descriptive analyses included?				9.7
10.3 Are stratified analyses included?				
10.4 Does the plan describe methods for adjusting for confounding?				9.7
10.5 Does the plan describe methods for handling missing data?				9.7.2
10.6 Is sample size and/or statistical power estimated?				9.7

Comments:

Section 11: Data management and quality control	Yes	No	N/A	Section Number
11.1 Does the protocol provide information on data storage? (e.g. software and IT environment, database maintenance and anti-fraud protection, archiving)				9.6
11.2 Are methods of quality assurance described?				9.8
11.3 Is there a system in place for independent review of study results?				9.6

Comments:

Section 12: Limitations	Yes	No	N/ A	Section Number

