ANNEX 3. ADDITIONAL INFORMATION

Supplemental Table 1: Variables available for DMP patients

DMP-key	Type	Meaning (German)	Meaning (English)
BETA2.LANG.BEDARF	Boolean ¹	Bedarf einer kurzfristigen langwirksamen Beta-2-Sympathomimetikatherapie	Need for a short therapy with long-acting beta-2-sympathomimetics
BETA2.LANG.DAUER	Boolean ¹	Bedarf einer dauerhaften langwirksamen Beta-2-Sympathomimetikatherapie	Need for a long-lived therapy with long-acting beta-2-sympathomimetics
BETA2_LANG.KEINE	Boolean ¹	Keine Langwirksame Beta-2-Sympathomimetikatherapie indiziert	No therapy with long-acting beta-2-sympathomimetics indicated
BETA2_LANG.KI	Boolean ¹	Langwirksame Beta-2-Sympathomimetikatherapie kontraindiziert	Long-acting beta-2-sympathomimetics contraindicated
ANTI_LANG.BEDARF	Boolean ¹	Bedarf einer kurzfristigen langwirksamen Anticholinergikatherapie	Need for a short therapy with long-acting anticholinergics
ANTI_LANG.DAUER	Boolean ¹	Bedarf einer dauerhaften langwirksamen Anticholinergikatherapie	Need for a long-lived therapy with long-acting anticholinergics
ANTI_LANG.KEINE	Boolean ¹	Keine langwirksame Anticholinergikatherapie indiziert	No anticholinergics indicated
ANTI_LANG.KI	Boolean ¹	Langwirksame Anticholinergikatherapie kontraindiziert	Anticholinergics contraindicated
COP.STATIONAER	Integer ²	Stationäre notfallmäßige Behandlungen wegen COPD seit der letzten Dokumentation (Anzahl)	Emergency inpatient hospitalizations due to COPD since last documentation
COP_EINWEISUNG.JA	Integer ²	COPD-bezogene Über- bzw. Einweisung veranlasst (Anzahl)	COPD-related referral / admission arranged (number of)
COP_EINWEISUNG.NEIN	Integer ²	COPD-bezogene Über- bzw. Einweisung nicht veranlasst (Anzahl)	No COPD-related referral / admission arranged (number of)
COP_EXA	Integer ²	Häufigkeit der COPD Exazerbation	Number of COPD-related hospitalizations
COP_SCHULUNG.NICHT_EMPF	Boolean ¹	Schulung nicht empfohlen	COPD-related training not recommended
COP_SCHULUNG.NM	Boolean ¹	Schulung nicht möglich (Fehlende Schulungskapazität, Krankenhausaufenthalt, private Gründe, ...)	COPD-related training not possible
COP_SCHULUNG.NW	Boolean ¹	Schulung nicht wahrgenommen	COPD-related training not participated
COP_SCHULUNG.OK	Boolean ¹	Empfohlene Schulung(en) wahrgenommen	Participated in recommended COPD-related training

¹Boolean variables represent one of two possible values (e.g. "1" or "0", "yes" or "no").

²Integer variables are variables that must take an integer value (0, 1, 2, ...)

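### In the COPD DMP-12 sensitivity analysis, a triple-therapy patient with no qualifying exacerbation and no FEV₁ value is scored as not in line with the 2012 guideline, exactly as if FEV₁ were 50% or more

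*Combined protocol and SAP*

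**What the plan says.** Section 9.3.2.2 (First Secondary, second sensitivity analysis) uses the COPD DMP-12 sample to judge the first triple prescription that is not at the index date. On who enters, it says: "patients for whom at least one DMP entry before date of prescription of above combination will be included". An FEV₁ value is not asked for.

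The section gives exacerbation history as the route to triple therapy under both guidelines and adds, for 2012 only, that "the 2012 guideline also recommended such a treatment in case a FEV₁<50% could be observed". The 2018 percentage then counts patients with too few claims exacerbations before the triple prescription date. The 2012 percentage adds two conditions: too few exacerbations in the DMP data, and "no documented FEV₁ value <50" per cent. The 2012 line has no date limit.

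The first sensitivity analysis, in the same section, takes FEV₁ information from the ICD-10 subcode and confines itself to patients who have one: "For patients for whom such a subcode is available, in this analysis, disease severity will be defined based on this information".

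On the clinical DMP data, Section 9.9 warns: "For a substantial part of the patients, these data might not be valid/available".

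**The concern.** The FEV₁ condition is worded as the absence of a low value. Both a recorded value of 50% or more and no recorded value at all satisfy it. The first is evidence that the 2012 FEV₁ route was closed. The second is no evidence either way, yet the rule gives both the same result.

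This matters because the DMP sample is where measured FEV₁ is brought in to credit the extra 2012 route, which the claims-only COPD-12 rule for triple therapy cannot do. Each missing value returns a no-exacerbation patient to the exacerbation-only test. Part of the reported 2012 percentage would then reflect documentation rather than prescribing. Section 9.3.2.2 also concedes that patients observed to mid-2018 cannot be expected to follow the 2018 guideline, so readers may well give the 2012 figure weight.

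**Working it through.** The plan states no expected non-adherence rate, FEV₁ completeness or number of triple starters for this analysis, so there is no figure to reproduce. The abstract expects about 4,000 DMP patients with a long-acting bronchodilator but does not say how many start triple therapy. The check is therefore a truth table of the written rule, followed by a misclassification calculation on assumed inputs.

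**Truth table.** The three conditions are joined by *and*. The last part reads "no inpatient exacerbation diagnoses as documented in the DMP dataset and no documented FEV₁ value <50" per cent.

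| Qualifying exacerbation (claims or DMP) | FEV₁ | Result under the 2012 rule |
|---|---|---|
| Yes | 40%, 60% or missing | In line |
| No | 40% | In line |
| No | 60% | Not in line |
| No | Missing | Not in line |

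The last two rows are the problem. It is confined to patients with no qualifying exacerbation in either source.

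**Size.** All inputs are assumptions:
- e = share of included triple starters with no qualifying exacerbation in claims or DMP data
- m = share of those with no FEV₁ value
- q = share with true FEV₁ below 50%, taken as equal in recorded and missing patients

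Formulas:
- Reported by the rule: e × (1 − (1 − m) × q)
- True: e × (1 − q)
- Overstatement: e × m × q
- Lower bound (all missing counted as below 50%): e × (1 − (1 − m) × q − m)
- Upper bound (all missing counted as 50% or more): the rule as written

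With e = 0.80, m = 0.30, q = 0.30:
- Reported: 0.80 × (1 − 0.21) = 63.2%
- True: 0.80 × 0.70 = 56.0%
- Overstatement: 0.80 × 0.30 × 0.30 = 7.2 points
- Bounds: 0.80 × (1 − 0.21 − 0.30) = 39.2%, to 63.2%

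Over e = 0.6 to 0.9, m = 0.1 to 0.5 and q = 0.2 to 0.5, the overstatement runs from 0.6 × 0.1 × 0.2 = 1.2 points to 0.9 × 0.5 × 0.5 = 22.5 points. It is zero if m = 0, or if no patient with a missing value truly has FEV₁ below 50%.

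**Opposite error.** Because the 2012 line has no date limit, an FEV₁ below 50% recorded only after triple therapy began could count as in line. If that reclassified 10% of the no-exacerbation patients in the same illustration, the reported figure would be 0.80 × (1 − 0.21 − 0.10) = 55.2%, against a true 56.0%. Two errors of this kind can cancel or reverse.

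**Why the unassessable patients cannot simply be dropped.** Removing only the no-exacerbation patients without FEV₁, while keeping every exacerbation patient, gives (0.80 × 0.70 × 0.70) / (1 − 0.80 × 0.30) = 0.392 / 0.76 = 51.6%. That is below the true 56.0%.

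**The case against.** Several points on the other side stand.

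- **Missing FEV₁ alone does not make a patient non-adherent.** A qualifying exacerbation in either source settles the matter. A reader who looks only at the FEV₁ clause could miss this.
- **A general missing-data rule may exist.** The Annex 2 checklist item "10.5 Does the plan describe methods for handling missing data" is answered yes and points to Section 9.7.2, which cannot be read in the public document. The abbreviation list includes LOCF, which the visible text does not use. So one cannot say that the plan lacks a rule, only that the visible scoring rule assigns missing values a result.
- **The Section 9.9 warning is not specific to this sample.** It follows a sentence saying that clinical parameters exist only for DMP participants, so the patients it refers to may include non-participants. It makes missing FEV₁ plausible here but does not quantify it.
- **The first sensitivity analysis handles FEV₁ better.** It is limited to patients with the subcode. That helps the 2012 comparison in general but does not change how the DMP rule scores a missing value.

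Three stronger readings are tempting and unsupported. First, a reader might infer that the FEV₁ route could never be met, because the annex table headed "Supplemental Table 1: Variables available for DMP patients" shows 16 keys and none for FEV₁, although Table 1 in Section 9.1 refers to it. But the abstract and Sections 9.1, 9.3.2.2 and 9.4 all name FEV₁ as DMP information. The annex list also lacks weight, height, blood pressure and smoking status, which the abstract plans to report, and Section 9.1 describes a separate agreed variable list for extraction. Second, a reader might infer that the published 2012 percentage must be too high; the missing date limit prevents that conclusion. Third, a reader might suppose that the error carries into the logistic regression on guideline-conforming treatment in Table 4, but the documents do not say which classification that model uses.

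**Conclusion.** The point holds as a reading of the visible rule. In COPD DMP-12, a patient with no qualifying exacerbation and no FEV₁ value is scored the same as one with FEV₁ of 50% or more. The figure presented as the 2012 percentage is in effect the upper missing-value bound.

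The 1.2 to 22.5 point range is illustrative. It depends on the assumed shares and, for the reported and true percentages, on equal q in recorded and missing patients. Direction is fixed for this component only.

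The scope is narrow: one 2012 percentage in one sensitivity analysis. The primary objective, the 2018 percentage and the COPD-12 results are not shown to be affected. It is worth correcting because the remedy is cheap, but it does not threaten the study.

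**What to change.** In Section 9.3.2.2, for the COPD DMP-12 triple-therapy assessment:

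1. Count only FEV₁ values and exacerbations dated on or before the first triple prescription, for both guideline versions.
2. Report the number of patients with no qualifying exacerbation and no FEV₁ value as not assessable.
3. Lead with the 2012 percentage for the whole group as two bounds: those patients all counted as below 50%, and all counted as 50% or more.
4. Beside the bounds, give the percentage among all patients with an FEV₁ value, whatever their exacerbation history, with its denominator.
5. Reconcile Supplemental Table 1 with the sections that list FEV₁ as a DMP variable, and state whether Section 9.7.2 applies to this classification.

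The cost is a few sentences and extra table columns, using data the analysis already needs. The downside is a range in place of a single figure, and a smaller denominator for the FEV₁-available percentage.
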